	Primary Efficacy Evaluation: 
• Proportion of subjects achieving an objective skin response (complete response [CR] or partial response [PR]) of at least 4 months duration (ORR4) using the Modified Severity Weighted Assessment Tool (mSWAT) scoring.
Secondary:	
	Efficacy measures: 
• Progression-free survival (PFS).• Complete response rate (CRR).• Time to progression (TTP).• Time to maximal effect in skin (mSWAT).• Proportion of subjects achieving $\geq 50\%$ improvement in mSWAT of at least 28-days duration (ORR1).• Proportion of subjects achieving $\geq 50\%$ improvement in mSWAT from baseline at 28 days and at 4 months.• Time to $\geq 50\%$ improvement in mSWAT.• Duration of response in skin (no progression after achieving $\geq 50\%$ improvement in mSWAT).• Change in pruritus medication utilization from baseline and incidence of pruritus medication utilization.

- During the crossover portion of the study:
 - Proportion of subjects achieving an objective skin response (complete response [CR] or partial response [PR]) of at least 4 months duration (ORR4) using the mSWAT scoring (see [Appendix F](#)).
 - Progression-free survival (PFS).
 - Complete response rate (CRR).
 - Time to progression (TTP).
 - Time to maximal effect in skin (mSWAT).
 - Proportion of subjects achieving $\geq 50\%$ improvement in mSWAT of at least 28-days duration (ORR1).
 - Proportion of subjects achieving $\geq 50\%$ improvement in mSWAT from baseline at 28 days and at 4 months.
 - Time to $\geq 50\%$ improvement in mSWAT.
 - Duration of response in skin (no progression after achieving $\geq 50\%$ improvement in mSWAT).
 - Change in pruritus medication utilization from baseline and incidence of pruritus medication utilization.

Safety and Tolerability Evaluations:

- Incidence and severity of clinically significant adverse events (AEs) (including grade 3 and 4 AEs, treatment-related AEs, serious adverse events [SAEs], and AEs requiring discontinuation), physical examination findings, changes in electrocardiograms (ECGs), changes in laboratory parameters and changes in vital signs.
- Characterization of anti-drug antibody generation.

Pharmacokinetic Evaluation:

- Population PK parameters.
- During the crossover portion of the study:
 - Pharmacokinetic C_{\max} and trough concentration analysis

Study Design:

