7.1.7 Prior and Concomitant Medications

All medications (including over-the-counter medicines, herbal treatments, supplements, and vitamins) administered within 30 days before the first administration of study treatment (Day 1) through the End of Treatment Visit will be recorded on the eCRF, using generic names when possible. Additionally, any concomitant medications taken for MF will be recorded throughout the study until confirmation of disease progression. All medications taken for pruritus indication will be captured on a separate eCRF page.

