7.1.7.2 Prohibited and Limited Use of Concomitant Medications

Topical and systemic treatment for CTCL will be prohibited during the study, except in exceptional circumstances as noted below.

Systemic Corticosteroids

In principle, initiation of systemic corticosteroid treatment or increase in corticosteroid dose for CTCL-related symptoms is prohibited during the study. Subjects receiving a stable dose of oral prednisone of ≤ 10 mg daily (or steroid equivalent) at Screening are permitted to continue any such regimen, although the investigator should attempt to taper off or to decrease the dose to the

lowest dosage tolerable while on study. In specific cases, and only after Medical Monitor approval, a transient systemic corticosteroid therapy course for symptoms related or unrelated to CTCL, limited to 7 days per course, and no more than one course per 60 days is allowed.

Topical Corticosteroids and other Oral/Topical Medications

Subjects that enter the study on a stable dose of medium or low potency topical corticosteroids for the treatment of pruritus may continue use at the same dose, although the investigator should attempt to taper off or decrease the use to the lowest dosage tolerable while on study.

Initiation of new and transient topical high potency steroid therapy should be avoided unless needed to treat an acute non-CTCL condition. In this case, and only with Medical Monitor approval, a short course (≤ 7 days) of high potency topical corticosteroid is allowed, and not more than one short course per 60 days will be allowed.

Initiation of new and transient topical, low or medium potency steroid therapy and/or oral antihistamines for pruritus is permitted, but should be limited to 7 days per course, and no more than one course per 30 days.

Any new and transient use of topical corticosteroids should be recorded as a new medication in the concomitant medication or pruritus medication eCRF (depending on the indication), including the specific corticosteroid name, potency, formulation (ointment, cream, gel or lotion), indication and start and stop date.

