miRagen has evaluated topical corticosteroids potency used in all countries where SOLAR is being conducted. A comprehensive, but not exhaustive list of low, medium and high potency topical corticosteroid lotions, ointments, gels, solutions, foams and creams, as per miRagen's determination, is provided in [Appendix I](#). Though the determination of potency in few cases might slightly diverge from its clinical use in some countries, this list should be used to guide inclusion and exclusion criteria, prohibited medications, as well as exceptional new and transient use of topical corticosteroids during a subject's participation in this trial.

Use of topical emollients, moisturizers, camphor/menthol or pramoxine formulations (or other equivalent institutional standard of care therapies) should be limited where possible, but if used, should be recorded in the concomitant medication eCRF. Any use of other methods (herbal supplements, ice baths, etc.) to treat pruritus should be avoided, but if used, should likewise be recorded in the concomitant medication eCRF.

Nonsteroidal Anti-pruritic Medications

The use of new prophylactic systemic anti-pruritic agents is prohibited.

The use of new daily symptomatic systemic anti-pruritic agents is discouraged. **Under exceptional circumstances, and only after Medical Monitor approval**, these medications could be allowed. These medications include, but are not limited to doxepin, gabapentin, aprepitant, mirtazapine, selective serotonin reuptake inhibitors, or naltrexone.

Short and intermittent courses of symptomatic systemic anti-pruritic agents should be avoided (with the exception of antihistamines, as noted above) including but not limited to doxepin, gabapentin, aprepitant, mirtazapine, selective serotonin reuptake inhibitors, or naltrexone. However, in exceptional circumstances and with prior Medical Monitor approval, a short course (e.g. ≤ 7 days) of a new systemic anti-pruritic agent may be allowed. Any medications used to treat symptomatic pruritus should be recorded on the pruritus concomitant medication eCRF.

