10 ASSESSMENT OF SAFETY

10.1 Specification of Safety Parameters

Safety will be evaluated through continuous monitoring of AEs, vital signs, physical examinations, clinical laboratory measurements, and ECGs.

Management of Infusion-related adverse events:

Allergic events and/or infusion-related toxicities should be managed according to institutional guidelines. If institutional guidelines are not available, the following recommendations apply.

Rash, pruritus, urticaria and wheezing due to an infusion-related AE, may be treated with diphenhydramine hydrochloride and/or steroids as clinically appropriate. Anaphylaxis or anaphylactoid signs or symptoms may be treated with steroids and/or epinephrine as clinically indicated. Any concomitant therapies used must be recorded in the eCRF. The Medical Monitor should be consulted prior to the use of steroids whenever possible. Subjects should be treated in a facility equipped for cardiopulmonary resuscitation. Infusion-related reactions (fever, rigors) should be treated per institutional guidelines but may be treated with acetaminophen and diphenhydramine hydrochloride.

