12.4.4 Analysis of the Secondary Endpoints

The secondary endpoint of progression-free survival is defined as the time from randomization to the date of the earliest documented progression or death due to any cause.

Time to event analyses (Kaplan-Meier) will be done for PFS, time to \geq 50% mSWAT improvement, time to maximal effect in skin, duration of maintaining response in skin, CRR, and TTP. For responding subjects, duration of response and duration of \geq 50% improvement will be displayed.

Summary statistics for change from Baseline for mSWAT scores will be presented by treatment and visit.

The percent of subjects achieving $\geq 50\%$ improvement in mSWAT scores will be presented by treatment for:

- $\geq 50\%$ improvement for at least 28 days;
- $\geq 50\%$ improvement at 4 months;
- $\geq 50\%$ improvement at 28 days.

The N (%) of complete responses will be presented by treatment.

P-values generated from secondary analyses are supportive only. The mean change from baseline in use of pruritus medication will be presented by treatment and visit.

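### Nothing excludes treatment of infusion-related itch, possible only on cobomarsen in the randomized period, from the pruritus-medication efficacy endpoint

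*Combined protocol and SAP*

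**What the plan says.** Section 3.2.2 and the Synopsis list "Change in pruritus medication utilization from baseline and incidence of pruritus medication utilization" under efficacy measures, and repeat it for the crossover period. The only analysis given, in Section 12.4.4, is this: "The mean change from baseline in use of pruritus medication will be presented by treatment and visit". The same section adds: "P-values generated from secondary analyses are supportive only".

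Capture is by indication. Section 7.1.7 states: "All medications taken for pruritus indication will be captured on a separate eCRF page". It makes no exception by cause.

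Section 10.1, on managing infusion-related events, states: "Rash, pruritus, urticaria and wheezing due to an infusion-related AE, may be treated with diphenhydramine hydrochloride and/or steroids as clinically appropriate". It requires concomitant therapies to be recorded in the eCRF but does not name the page. Section 10.2.1 allows premedication at later infusions after a grade 2 infusion-related reaction and calls for it after grade 3.

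Section 7.1.7.2 also shapes itch medication. Subjects who enter on stable low or medium potency topical steroids for pruritus may continue, "although the investigator should attempt to taper off or decrease the use to the lowest dosage tolerable while on study". New daily systemic anti-pruritic agents are discouraged and allowed exceptionally "and only after Medical Monitor approval". Other new systemic agents may be allowed "in exceptional circumstances and with prior Medical Monitor approval, a short course". New low or medium potency topical steroids and oral antihistamines need no approval, within limits on course length and frequency.

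**The concern.** An endpoint that counts itch medication is meant to reflect how well each treatment controls the itch of mycosis fungoides. Under the text as it stands, a subject given diphenhydramine for itch during an infusion has taken a medication for pruritus and can enter the count. Vorinostat is oral (Section 4.3), so no subject on that arm can contribute such use in the randomized period. An arm-specific adverse reaction could then be read as poorer efficacy.

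This matters somewhat more because no other listed efficacy measure addresses itch. Section 2.2 describes pruritus as a major symptom and credits vorinostat with a significant effect on it, so readers will look at this comparison.

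**Working it through.** The plan states no figure for this endpoint, so there is none to reproduce. The check is first of the text, then of scale under assumed rates.

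**Text**

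1. Sections 3.2.2 and 12.4.4 analyse pruritus-medication use without restricting the reason for use.
2. Section 7.1.7 collects it by indication, without restricting the cause.
3. Section 10.1 names pruritus as an infusion-related event that may be treated with medication.
4. Section 4.3 gives cobomarsen by infusion and vorinostat by mouth.

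Together these allow use in one arm that has nothing to do with disease itch. Premedication is less clear: Section 10.2.1 does not name the drug or its indication, so its place depends on how sites code it. If it is coded to pruritus, one reaction could generate repeated records, because infusions become weekly after the first days.

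**Scale**

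Inputs:
- 63 subjects per arm (Section 12.5.1).
- p, the proportion needing itch medication for disease, taken as equal in both arms. Assumed: 20%, 40%, 60%.
- x, the proportion of cobomarsen subjects treated for infusion-related itch, taken as independent of disease need. Assumed: 5%, 10%, 20%.

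Apparent cobomarsen incidence = 1 − (1 − p)(1 − x), so the spurious excess is (1 − p)x.

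For p = 40%:
- x = 5%: 1 − 0.60 × 0.95 = 0.43, an excess of 3 points
- x = 10%: 1 − 0.60 × 0.90 = 0.46, an excess of 6 points
- x = 20%: 1 − 0.60 × 0.80 = 0.52, an excess of 12 points

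The table gives the excess in percentage points. In brackets is the chance that a normal-approximation test of two proportions, 63 per arm, reaches nominal two-sided p < 0.05 against cobomarsen with no true difference in disease itch. Without the artefact that chance would be 2.5%.

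| p | x = 5% | x = 10% | x = 20% |
|---|---|---|---|
| 20% | 4 (7.8%) | 8 (18.1%) | 16 (51.6%) |
| 40% | 3 (5.3%) | 6 (10.0%) | 12 (27.0%) |
| 60% | 2 (4.2%) | 4 (6.7%) | 8 (15.2%) |

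The bracketed values are for scale only, since Section 12.4.4 specifies no test of incidence. The effect on the planned mean change by visit cannot be calculated, because the unit of use is not defined.

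**The case against.** The strongest reply has three parts.

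- **Recording.** Section 10.1 names no eCRF page, and a site might code the drug to the infusion reaction instead of to pruritus. This stands: the documents show that nothing excludes such use, not that it will be counted. But a count that depends on each site's coding is itself a reason for a rule.
- **Stakes.** The endpoint is supportive, lies outside the ORR4-then-PFS step-down in Section 12.2, and any bias runs against the sponsor's own product. A single day's treatment would move a mean by visit very little. All of this stands and limits the weight of the point.
- **Deferral.** Sections 12.1 and 12.4 leave room for a later SAP to settle the definition. It can, but only if the reason for use has been collected.

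A reader might go further and infer that the endpoint is dictated by the taper instruction and by an arm-aware sponsor monitor. The documents do not support that. Section 7.1.7.2 lets subjects start low or medium potency topical steroids and oral antihistamines without approval, so a subject refused a systemic agent can still register as a user. Multiplying total need by an assumed approval rate in each arm would therefore be invalid. No text suggests that approvals differ by arm, and the monitor's knowledge of assignment is only inferred from the open-label design.

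A reader might also infer that a fall from baseline is built into the crossover. The taper is an attempt, down to what the subject tolerates. It applies to both arms, and crossover subjects were already under it during the randomized period.

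**Conclusion.** The point holds in a limited form. As written, medication for infusion-related itch can enter a secondary efficacy measure, and in the randomized period it can do so only on cobomarsen. The bias in incidence would run against cobomarsen. It would be 3-12 percentage points if disease-related need is 40% in each arm and 5-20% of cobomarsen subjects are treated for infusion-related itch, or 2-16 points if need lies between 20% and 60%. These rates are assumptions; the documents give none. Section 2.1.3.2 mentions pruritus among the Phase 1 dose-limiting toxicities but does not say that it was infusion-related, so it does not supply a rate.

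The taper and approval rules support a narrower conclusion: within-arm change from baseline mixes drug effect with protocol instruction and cannot by itself show benefit, least of all in the single-arm crossover. They do not show a bias between the randomized arms. Neither the primary nor the key secondary result is affected.

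**What to change.** In Sections 3.2.2 and 12.4.4:

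1. Exclude from the efficacy endpoint any medication given for an infusion-related AE or as infusion premedication. Identify it by a reason-for-use field on the pruritus page or by a link to the AE page.
2. Report the excluded use under safety.
3. Tabulate all pruritus-medication use, without the exclusion, as a sensitivity analysis.
4. State that within-arm change from baseline, including in the crossover period, is descriptive only, in view of the taper and approval rules in Section 7.1.7.2.

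Tapers that are achieved should stay in the endpoint, since reduced need for medication is part of what it measures. Requests for medication should not replace use as the event: they would measure something else and are no less open to knowledge of treatment arm.

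The cost is slight extra data entry and one extra table. No change to treatment or its management is involved. The rule should be fixed before comparative data on this endpoint are tabulated.

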2 BACKGROUND INFORMATION AND SCIENTIFIC RATIONALE

2.1 Background Information

2.1.1 Cutaneous T-cell Lymphoma

Cutaneous lymphomas of T-cell or B-cell origin comprise approximately 3.9% of all non-Hodgkin's lymphomas. Of these, approximately 53% are of T-cell origin (cutaneous T-cell lymphoma or CTCL). The prevalence of the disease in the United States (US) is estimated at 30,000 cases ([Cutaneous Lymphoma Foundation 2014](#)), although this estimate is acknowledged to be low due to the difficulty of diagnosis in the early stages of the disease. The annual age-adjusted incidence of CTCL in the US is estimated at 6.4 to 9.6 cases per million people ([Jawed et al. 2014a](#)).

CTCL presents in the skin with no evidence of extracutaneous disease at the time of diagnosis. Mycosis fungoides (MF) is the most prevalent subtype of CTCL, accounting for 50-70% of all primary cutaneous T-cell lymphomas. The second most prevalent subtype is Sézary syndrome (SS), comprising 15% of CTCL cases. MF is characterized by proliferation of atypical small- to medium-sized T lymphocytes with cerebriform nuclei that form patches, plaques, or nodular tumors in the epidermis. MF typically affects older adults (median age of diagnosis: 55 to

60 years) and has an indolent clinical course where patches and plaques precede or are concurrent with the formation of tumors. In some late tumor-stage cases, lymph node and visceral organ involvement are observed. During tumor-stage MF, the dermal infiltrates become more diffuse and the epidermotropism of the atypical T-cells may be lost. In contrast, SS is a more aggressive, leukemic form of CTCL, characterized by widespread redness and scaling of the skin (erythroderma), enlarged lymph nodes, and malignant cells in the peripheral circulation (Jawed et al. 2014a; Yamashita et al. 2012).

The trigger for atypical T-cell epidermotropism is unclear. Infectious agents such as the human T-cell lymphotropic virus type 1, Epstein-Barr virus, cytomegalovirus, and *Staphylococcus aureus* have been hypothesized as possible triggers, but a definitive link with any of these agents has not been established. Chronic antigen stimulation, due to inflammation or trauma has also been hypothesized as a driver of CTCL pathogenesis (Burg et al. 2002; Tan et al. 1974), as have medications (Samimi et al. 2013). Molecular analyses of tumor stage MF have revealed significant changes in gene expression compared to normal skin, inflamed skin and normal T-cells (van Kester et al. 2012), although the genetic or epigenetic origin of these differences in gene expression are unknown. Advanced stage and erythrodermic MF patients can exhibit immunosuppression, as demonstrated histopathologically by loss of T-cell surface antigens in patients as the disease progresses (Jawed et al. 2014a; Jawed et al. 2014b). Significant differences in the gene expression profiles of MF and SS cells have also been observed, consistent with a distinct pathogenesis for these variants of CTCL (Campbell et al. 2010; van Doorn et al. 2009).

Currently there are no therapies that cure or prolong the survival of late-stage CTCL patients (Prince et al. 2009). Treatments for CTCL patients at an early-stage of disease are palliative and non-aggressive with careful physician monitoring. More advanced stage CTCL patients are typically treated with systemic drugs, such as retinoids (bexarotene) or histone deacetylase inhibitors (vorinostat or romidepsin), phototherapy or total skin electron beam irradiation. Patients with MF expressing the CD30 cell surface antigen may be eligible for treatment with brentuximab vedotin, an anti-CD30 monoclonal antibody-cytotoxic drug conjugate. Multiagent chemotherapy or radiotherapy is reserved for patients with advanced, refractory disease and can result in partial disease regression but not full eradication. Many treatments have serious side effects or lose efficacy over time. Thus, there remains an unmet medical need for new therapies to treat CTCL.

2.1.2 Human microRNA-155-5p

2.1.2.1 *miR-155-5p in Normal Physiology and Immune Response*

miR-155-5p is a microRNA (miRNA) that, in humans, is encoded by the MIR155 host gene, MIR155HG. This gene, also known as BIC (B-cell integration cluster) was originally identified as a common site for retroviral insertion in avian leukosis virus-induced lymphomas (Tam et al. 1997). The 23 nucleotide, single-stranded miR-155-5p is encoded in exon 3 of the parent gene. The sequence of miR-155-5p is highly conserved across species. In non-human primates, the sequence of the microRNA is identical to the human sequence, while in mice and rats, the C at position 12 in the human sequence is replaced with a U in the rodent miRNA (miRbase, <http://www.mirbase.org/>).

miR-155-5p is expressed in hematopoietic cells including B-cells, T-cells, monocytes and granulocytes (Landgraf et al. 2007). miR-155-5p is an essential molecule in the control of both myelopoiesis and erythropoiesis. This miRNA is highly expressed in hematopoietic stem-progenitor cells at an early stem-progenitor stage and blocks their differentiation into a more mature hematopoietic cell (e.g., lymphocyte, erythrocyte). miR-155-5p expression progressively decreases as cells mature along these lineages and is ~200-fold lower in mature hematopoietic cells (Masaki et al. 2007; Lu et al. 2014; Burocchi et al. 2015; Kroesen et al. 2015).

miR-155-5p plays an important role in mediating inflammatory and immune responses. Mice lacking miR-155-5p show a normal number and distribution of T- and B-lymphocyte subpopulations, but display a deficient immune response, specifically in regulating T helper cell differentiation and the germinal center reaction to produce an optimal T-cell dependent antibody response (Rodriguez et al. 2007; Thai et al. 2007). miR-155-5p controls differentiation of CD4⁺ T-cells into the T helper type 1 (Th1), Th2, and Th17 subsets of T helper cells, and affects the development of regulatory T-cells (Treg) (Baumjohann et al. 2013). miR-155-5p also regulates effector and memory CD8⁺ T-cell responses to viral infection (Dudda et al. 2013; Gracias et al. 2013), as well as normal B-cell differentiation and antibody production. In humans, miR-155-5p expression is low in nonlymphoid organs as well as in resting, naïve CD4⁺ T-cells. miR-155-5p expression is greatly enhanced by antigen receptor stimulation of B- and T-cells (Tam 2001; Haasch et al. 2002; van den Berg et al. 2003; Rodriguez et al. 2007; Thai et al. 2007; Vigorito et al. 2007; Banerjee et al. 2010), and by Toll-like receptor agonist stimulation of macrophages and dendritic cells (Taganov et al. 2006; O'Connell et al. 2007; Ceppi et al. 2009; Mao et al. 2011). MIR155HG activation involves both AP1- and NFκB-mediated mechanisms.

2.1.2.2 *miR-155-5p in Cutaneous T-Cell Lymphoma, Mycosis Fungoides Subtype*

miRNAs have been reported to be differentially expressed and potentially involved in the pathogenesis of CTCL. miR-155-5p is among the miRNAs most up-regulated in MF (Kopp et al. 2013a; Kopp et al. 2013b). Conversely, a distinct subset of dysregulated miRNAs is observed in SS, and miR155-5p is not up-regulated in this subtype of CTCL (Ballabio et al. 2010).

Increased miR-155-5p in MF patient skin biopsies compared to control skin biopsies has been reported by several groups (van Kester et al. 2011; Maj et al. 2012; Kopp et al. 2013b; Moyal et al. 2013). In one study, miR-155-5p levels were more than 4-fold higher in tumor-stage biopsies compared to early MF biopsies (Moyal et al. 2013), suggesting that miR-155-5p levels may be correlated with disease progression. In a second study to further define the specific cell types that express miR-155-5p, the miRNA was found by *in situ* hybridization to be expressed in both malignant and non-malignant T-cells in the CTCL lesions (Kopp et al. 2013b).

miR-155-5p dysregulation is linked to signaling pathways that have been implicated in CTCL pathogenesis. Specifically, malignant T-cells are reported to constitutively express the interleukin (IL)-2 receptor complex and the associated Janus kinases (JAK) that activate transcription via the STAT proteins. miR-155-5p expression has been linked to the STAT5 pathway in CTCL malignant T-cells in culture: chromatin immunoprecipitation experiments found STAT5 to be associated with the promoter of MIR155HG. Inhibition of the JAK/STAT pathway resulted in down regulation of miR-155-5p expression, and treatment of cells with cytokines activating STAT5 resulted in increased miR-155-5p levels (Kopp et al. 2013a). These results suggest that miR-155-5p may play a role in the pathogenesis of CTCL. In support of this hypothesis, the authors showed that CTCL cells grown in the presence of an inhibitor to miR-155-5p had a reduction in cellular proliferation (Kopp et al. 2013a). These data suggest that inhibition of miR-155-5p may have therapeutic effects by affecting the malignant T-cells of MF patients.

2.1.3 **Investigational Product: Cobomarsen**

miRagen has identified an antagonist of miR-155-5p, cobomarsen (also referred to by the company code, MRG-106), by screening a panel of synthetic oligonucleotides for inhibitory activity as measured by target gene de-repression in cultured cells. Cobomarsen is designed to interact with miR-155-5p through base-pairing complementarity to competitively inhibit the interaction of miR-155-5p with its mRNA targets.

In vitro pharmacology data demonstrate that exposure of cultured miR-155-5p-expressing MF cell lines to cobomarsen results in de-repression of miR-155-5p direct mRNA targets. Further, two of three MF cell lines that were exposed to cobomarsen in culture showed significantly reduced proliferation and increases in protein markers of apoptosis. An SS cell line that does not express high levels of miR-155-5p was not similarly responsive to the drug. These data support the further evaluation of cobomarsen for its safety, tolerability and potential to provide therapeutic benefit in patients with MF.

